5.0 REQUIRED EVALUATIONS, TESTS, AND OBSERVATIONS

5.1 Pre-Study and Study Activities

FOCUS GROUPS AND FEASIBILITY STUDY ACTIVITIES

STUDIES ACTIVITIES	Pre-Study	Focus Group Phase	Feasibility Study Phase	Off Study
Screening	X	X	X	
Consent	X	X	X	
Expert Panel – virtual meetings with stakeholders & key investigators		X		X
Stakeholder Feedback – virtual focus groups		X		X
Preliminary Content Adaptation - co-investigators only	X	X		
Iterative Content Adaptation – virtual focus groups		X		X
Finalized adaptation – virtual focus groups		X		X
Culturally Adapted CBT + active tDCS or Culturally Adapted CBT + sham for 20 min sessions twice a week for 6 weeks			X	X
Completion of Questionnaires			X	

6.0 CRITERIA FOR REMOVAL FROM PROTOCOL

6.1 Off Study Criteria

Death

Lost to follow-up

Request of the Patient/Parent

Discretion of the Study PI, such as the following

- The researcher decides that continuing in the study would be harmful
- The participant misses so many appointments that the data cannot be used in the study
- The participant's condition gets worse
- New information is learned that a better treatment is available, or that the study is not in the participant's best interest
- Study evaluations are complete

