Adverse event monitoring: Patient reports of AEs will be surveyed weekly, with symptoms reported for the prior tDCS sessions. Information will be collected by incident participant reporting and direct questioning using the patient report of incidence of side effects (PRISE).⁸⁵ Side effects will be assessed during weekly sessions. The PRISE assesses the presence of side effects for several biological systems. For each system (skin, nervous, eyes/ears, sleep, other), participants indicate the presence of a side effect, and if present, the tolerability of the side effect (tolerable or distressing). The PRISE includes commonly reported side effects of tDCS: tingling, itching sensation, burning sensation, pain, headache, fatigue, difficulty concentrating, and nervousness.⁸⁶ Participants will also be asked to report any other symptoms experienced during the tDCS session.

Figure 4a. Study Schema – Virtual Focus Groups

[figure not shown]
[figure not shown]

Figure 4b. Study Schema – Feasibility Pilot Study

4.2 Study Procedures:

All cultural adaptation processes will occur separately, but in parallel, for non-Hispanic Black and Hispanic participants. See detailed descriptions of procedures in 4.1 Design and Study Overview above.

Expert Panel via virtual meetings - 2 to 4 (1) hour virtual meetings with non-Hispanic Black and Hispanic parents and young adult survivors of childhood cancer and key study investigators. Sessions will be audio-recorded and transcribed verbatim.

Stakeholder Focus Group via virtual focus groups - (2-4) 45-minute sessions with non-Hispanic Black and Hispanic adolescent survivors of childhood cancer. Sessions will be audio-recorded and transcribed verbatim.

Preliminary Content Adaptations – based on results of qualitative analysis of stakeholder feedback.

Iterative Adaptation Process via virtual focus groups - (2-4) 45-minute sessions where adaptations will be presented to lived experience stakeholders (non-Hispanic Black and Hispanic survivors of childhood cancer with chronic pain). Sessions will be audio-recorded and transcribed verbatim.

Feedback meetings via virtual focus groups – (2-3) with 5-7 non-Hispanic Black and 5-7 Hispanic adolescent survivors who participated in previous sessions to review final program adaptations. Sessions will be audio-recorded and transcribed verbatim.

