4.3 Study Measures/Observations

Participants in both the focus group and feasibility study will be asked to fill out screening questions as described in the paragraph below.

Demographics: Participants will complete a consent to contact form and, if willing, will complete demographics questions during the screening process to obtain ethnicity, race, and other information needed to target recruitment to meet enrollment goals. If we are unable to confirm diagnosis or other screening information needed to confirm eligibility, study staff will ask the parent/guardian to sign a medical release form to obtain pertinent medical records.

Participants in the feasibility study will complete the outcomes measures listed below (e.g. pain intensity, functional disability) and parents will complete measures of SES, anxiety, depression, and their child's perception of pain and medication use at baseline and post-intervention (Table 2)

Pain intensity and pain interference: The *Brief Pain Inventory-Short Form* (BPI) includes a 4-item pain severity scale.⁸⁷ Participants rate their worst and least pain in the last week, average pain, and current pain.⁸⁸ The BPI pain intensity has good internal consistency in survivors of childhood cancer ($\alpha=0.87$).⁸⁹ This measure includes a body diagram to allow participants to indicate where they experience the most pain. This will be used to inform placement of the anodal tDCS electrode (i.e., right vs. left DLPFC).^{90, 91}

Pain catastrophizing: The *Pain Catastrophizing Scale, Child version* (PCS-C)⁹² is a 13-item self-report measure of overly negative attitudes of pain and it consists of three scales of rumination, magnification, and helplessness. Higher scores indicate more pain catastrophizing.⁹³ This measure has good reliability (Cronbach's $\alpha=0.90$) in a clinical sample of children and adolescents with chronic or recurrent pain.⁹² The *Pain Catastrophizing Scale, Parent version* (PCS-P) is a

modified version of the PCS-C based on parent report of their own catastrophizing related to their child's pain. It assesses the same three factors of rumination, magnification, and helplessness.^{94, 95}

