7.0 SAFETY AND ADVERSE EVENT REPORTING REQUIREMENTS

7.1 Adverse Events (AEs)

Adverse events will be monitored from the start of the study. Participants will be instructed to report all AEs during the study and will be assessed for the occurrence of AEs throughout the study. Weekly PRISE forms will be completed.

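### Section 6.1 lets the PI take a participant off study for harm or worsening, and the visible text plans no adverse event follow-up or post-intervention assessment after such a removal

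*Combined protocol and SAP*

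**What the plan says.** Section 6 has a single subsection, 6.1 Off Study Criteria. Besides death, loss to follow-up and family request, it allows removal at "Discretion of the Study PI, such as the following". The examples that follow include "The researcher decides that continuing in the study would be harmful" and "The participant's condition gets worse". No other section defines a status in which tDCS or CBT stops while observation goes on.

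On adverse events, Section 4.1 says "Side effects will be assessed during weekly sessions", "with symptoms reported for the prior tDCS sessions". It adds that "Information will be collected by incident participant reporting and direct questioning". Section 7.1 says participants "will be assessed for the occurrence of AEs throughout the study" and that PRISE forms are completed weekly. Section 7.3 repeats the weekly survey and sets out what the PI does on learning of an event. None of these sections gives a follow-up period after removal, or follow-up until an event resolves.

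On outcomes, Section 4.3 places the questionnaires, including parents' report of "medication use at baseline and post-intervention (Table 2"), at two time points. Table 2 lists the acceptability items among them. No early-termination assessment is described. For dropouts, Section 9.0 plans to collect reasons and information on unfavourable acceptability, but gives no timing for someone removed early.

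**The concern.** Harm and worsening are related to outcome. If a participant leaves the study on either ground and nothing more is collected, three things are exposed.

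- **Safety.** Participants are aged 10 to 17 and use stimulation remotely. The outcome of the event that led to removal may never be actively sought.
- **R33 planning.** Section 9.0 compares mean change in pain intensity and functional disability between active and sham with a two-sample t-test, and uses the estimate for the next trial's power calculation. A participant removed for worsening has no post-intervention score, and those who remain are probably the better-faring ones. The worsening ground is not limited to pain, so the link to pain scores is likely but not certain.
- **Acceptability.** Section 9.0 calls the intervention not feasible as designed if more than 50% rate it unacceptable. Ratings from removed participants are among the likeliest to be unfavourable.

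**Working it through.** **1. The plan's own figure.** Section 9.0 requires 23 completers of 30, with a 95% exact lower bound of 0.61. The one-sided Clopper-Pearson bound is the 0.05 quantile of Beta(23, 8), which is 0.606 and rounds to 0.61. The figure reproduces. The rule counts sessions (9 of 12 tDCS and 4 of 6 CBT) in a fixed sample of 30. Anyone removed before reaching those counts is a non-completer, and no post-removal questionnaire is needed. The rule is not affected.

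**2. When the gap opens.**

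| Situation | Status under 6.1 | Weekly PRISE/AE survey | Post-intervention questionnaires |
|---|---|---|---|
| Stimulation stops, PI does not remove | On study | Continues (7.1 and 7.3 do not tie it to a session) | Not excluded |
| PI uses the harm or worsening ground | Off study | No stated continuation | No stated collection |

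Only the second row is a gap. After removal there may still be participant-initiated reports, PI action on a known event, and a recorded reason for dropout. None of these is active contact until resolution, a pain or function score, or an acceptability rating.

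**3. Bias in the active-versus-sham difference.** Section 4.1 gives 5 per arm in each of three groups, so 15 per arm. The documents give no removal rate. I assume k = 1, 2 or 3 removals, all in one arm, whose change scores average 1 SD worse than those remaining in that arm.

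- Shift: the observed arm mean exceeds the full-arm mean by (k/15) × 1 SD.
- Half-width of the 95% confidence interval: t(0.975, 28 − k) × √(1/15 + 1/(15 − k)) SD.

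| k | Shift (SD) | Half-width (SD) | Shift / half-width |
|---|---|---|---|
| 0 | 0 | 2.048 × 0.3651 = 0.748 | – |
| 1 | 1/15 = 0.067 | 2.052 × 0.3716 = 0.762 | 9% |
| 2 | 2/15 = 0.133 | 2.056 × 0.3789 = 0.779 | 17% |
| 3 | 3/15 = 0.200 | 2.060 × 0.3873 = 0.798 | 25% |

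The direction follows the arm with the removals: active looks better if they are in active, sham if in sham. Removals balanced between arms largely cancel.

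As an upper bound, suppose exactly the k worst changers are removed. With normal scores, the expected sum of the k most extreme of 15 values is 1.736, 2.984 and 3.932. Dividing by the number remaining gives 1.736/14 = 0.124, 2.984/13 = 0.230 and 3.932/12 = 0.328 SD.

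**4. Acceptability.** Assume the denominator is those who give a rating, which the plan does not state.

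- True count 16/30 = 53.3%, which fails the rule. One unrated removal among the 16 gives 15/29 = 51.7%, still a fail. Two give 14/28 = 50.0%, which is not above 50%, so the rule is passed.
- True count 17/30 = 56.7%. Three unrated removals give 14/27 = 51.9%. It takes four (13/26 = 50.0%) to change the result.

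The effect therefore matters only close to the threshold.

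**The case against.** The strongest reply is that the route proposed below is already open. Removal is discretionary, and missing or stopping stimulation is not an off-study criterion. Sections 7.1 and 7.3 require the weekly survey without tying it to a session. A reader might infer from 6.1 that any child who stops stimulation because of harm is dropped and unobserved, or that the PI must remove such a child. The documents support neither reading. The harm ground also speaks of continuing in the study, not of continuing stimulation, so on its literal wording it may be meant for cases where participation itself is the problem. All of this stands, and it confines the point to removals actually made on these grounds.

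Two further replies concern size. The protocol summary describes tDCS side effects as transient and no more frequent than with placebo, which suggests few removals and no strong imbalance between arms. The change-score comparison is declared unpowered, and acceptability is not among the three listed milestones for moving to R33. These also stand.

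Finally, the consent pages are not available here and may contain wording on withdrawal and follow-up. The absence can be asserted only for the visible text.

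What remains is that 6.1 offers off-study removal as a response to worsening, and that following it loses data for reasons tied to outcome. The PI's freedom to do otherwise does not tell the PI which course to prefer, or what to collect after a removal.

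**Conclusion.** The point holds in a limited form, as an improvement that should be made. When the off-study ground is used for harm or worsening, the visible text provides no active adverse event follow-up, no post-intervention score and no acceptability rating.

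The bias illustrated above is systematic but well inside the noise of the comparison. It rests wholly on assumed removals in one arm and an assumed 1 SD deficit. The acceptability result could change only near 50%, and only if unrated participants leave the denominator.

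A reader might infer that the main feasibility conclusion is at risk. It is not, because the completion rule needs no data after removal. The safety part has no number attached: it concerns knowing how an event ended in the few children removed because of it.

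**What to change.** Amend Section 6 so that, with consent or assent, the default response to worsening or to harm from the intervention is to stop tDCS/CBT while the participant stays on study. For these participants:

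- continue remote PRISE/AE contact until the event resolves or stabilises;
- collect the planned post-intervention questionnaires, including acceptability;
- analyse the scores in the arm as assigned, and count the ratings in the acceptability rule.

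Keep off-study removal for cases where study participation itself, including follow-up contact, would be harmful. Leave the other criteria unchanged.

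The cost is a short amendment and a few extra remote contacts. It adds no instruments, visits or participants. It does not recover data from families who withdraw or are lost, and it has to be in place before a removal occurs.

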7.0 SAFETY AND ADVERSE EVENT REPORTING REQUIREMENTS

7.1 Adverse Events (AEs)

Adverse events will be monitored from the start of the study. Participants will be instructed to report all AEs during the study and will be assessed for the occurrence of AEs throughout the study. Weekly PRISE forms will be completed.

7.2 Definitions

Adverse Event (AE): Any untoward medical occurrence associated in a study participant after the beginning of the study. Adverse Events will be graded by the NCI CTC AE version 5.0. Participants will be instructed to report all AEs during the study and will be assessed for the occurrence of AEs throughout the study.

Serious Adverse Event (SAE): Any adverse event temporally associated with the subject's participation in research that meets any of the following criteria:

- results in death;
- is life-threatening (places the subject at immediate risk of death from the event as it occurred);
- requires inpatient hospitalization or prolongation of existing hospitalization;
- results in a persistent or significant disability/incapacity;
- results in a congenital anomaly/birth defect; or
- any other adverse event that, based upon appropriate medical judgment, may jeopardize the subject's health and may require medical or surgical

intervention to prevent one of the other outcomes listed in this definition.

7.3 Handling of Adverse Events (AEs) and Deaths

Recording of Adverse Events and Serious Adverse Events: Adverse events of all types will be recorded in the database.

Reporting Adverse Events and Serious Adverse Events:

Adverse events will be surveyed weekly. Event information will be collected using a modified version of patient report of incidence of side effects (PRISE: see description above)

The St. Jude PI, upon awareness of an event, will determine the seriousness of AEs and ensure that all UPs are entered into the electronic submission system (iris) within 10 days. All (pertinent, as in *recording* above) AEs, serious or not, will be recorded in a log, spreadsheet, or report and submitted to the St. Jude IRB at the time of continuing review.

Unanticipated Problems (UPs): The St. Jude PI will refer to St. Jude Human Research Protection Program (HRPP) Policy 01.720 for definitions and specifics for reporting of unanticipated problems to the St. Jude IRB. The St. Jude IRB reports UPs to BIMO as per 21 CFR 56. The UP policy link follows:

[REDACTED]

Collaborating sites:

Report Serious Adverse Events as defined in section 7.2 internally per your IRB of record's policy **and** to the St. Jude Principal Investigator as soon as possible.

Report Unanticipated Problems to your IRB of record per policy **and** to the St. Jude Principal Investigator within 15 days.

Sharing of SAEs:

The St. Jude PI will ensure that all unexpected, possibly related Serious Adverse Events on study are shared with all sites. Collaborative sites will

share SAEs based on guidelines of CTA SOP 28 for more details. Link:
[REDACTED]

Deaths: Deaths meeting reporting requirements are to be reported immediately to the St. Jude IRB, but in no event later than 48 hours after the investigator first learns of the death.

7.4 Process for Communicating Study-Wide Adverse Events

The study PI will document their plan for obtaining adverse event information from a collaborator, and for disseminating study-wide adverse event information to the collaborators.

8.0 DATA COLLECTION, STUDY MONITORING, AND CONFIDENTIALITY

8.1 Data Collection

Electronic case-report forms (e-CRFs) will be completed by the St. Jude Clinical Research Associates or the site Study Coordinator. Data from the participant's record will be entered directly into a secure study-specific database. Instructions for data entry are outlined in the database.

Data management will be supervised by the ADAPTED study team. Protocol-specific data and adverse events will be recorded in the electronic database, ideally within 2 to 4 weeks of the study procedure. All questions will be directed to the Principal Investigator, [name], PhD., or designee and will be reviewed at regularly scheduled working meetings.

Regular summaries of protocol events will be generated for the PI and the Department of Biostatistics to review.

8.2 Data Collection Instructions for Collaborating Sites

Collaborating sites may collect data either by using Case Report Forms or by remote electronic data entry. Timeframes for entry of study data or completion of case report forms will be outlined so that study data may be obtained in a timely and consistent manner.

When CRFs are used, they will include the name and contact information of the person to whom the forms are to be sent.

8.3 Study Monitoring- Non-Therapeutic Risk Categories

This study is considered low risk for monitoring purposes. The Principal Investigator (PI) and study team are responsible for ensuring participant eligibility and protocol compliance. The study team will hold meetings as needed to review case histories or quality summaries on participants and will generate minutes which are signed by the PI.

CTO will review up to 10% of the study participants the first year for life status, status on study, and the appropriateness of the informed consent and eligibility processes. During this monitoring, the monitor will verify regulatory documentation pertinent to the study, all Serious Adverse Event reports, and Age of Majority consenting on all study participants. St. Jude affiliates and domestic collaborating study sites will be monitored remotely, in the same method as St. Jude, by the St. Jude Monitor. If there are no unresolved issues, no further monitoring will be performed. The PI and study team will be responsible for ensuring protocol and regulatory compliance. The Monitor will generate a follow-up letter which is shared with the Principal Investigator, study team, and the Internal Monitoring Committee (IMC).

Protocol continuing reviews by the Institutional Review Board (IRB) and Scientific Review Committee (CT-SRC) will occur at least annually. In addition, Unanticipated Problems and/or Serious Adverse Event reports are reviewed by the IRB.

8.4 Confidentiality

Confidentiality will be maintained. Data forms will be kept in locked file cabinets, in locked office space, accessed only by study staff on an “as needed” basis. Data files will be de-identified, linked by a participant identification number to a separate secure database. Data files downloaded for statistical analyses will not contain personal identifiers.

The medical records of study participants may be reviewed by the St. Jude IRB, FDA, clinical research monitors, etc.

9.0 STATISTICAL CONSIDERATIONS

The primary objective Qualitative analysis plan for focus groups: We will develop a codebook using *a priori* codes based on key domains and components from the literature,⁸⁰ as well as novel codes inductively derived through transcript review. Two coders will independently code focus group transcripts and meet regularly to resolve discrepancies and evaluate inter-rater reliability. Thematic content analysis will focus on identifying culturally specific adaptations and will be used to modify intervention content. MAXQDA software will be used for data management and processing. Given the iterative nature of our approach and the need for timely adaptation of the intervention, a rapid qualitative analysis technique¹¹⁷ will be used to summarize and analyze transcript data. Rapid analysis is being increasingly utilized in implementation science research and has been demonstrated to yield results similar to in-depth qualitative analytic methods.^{118, 119} Our analysis will focus on the 3 key domains of content, methodology, and procedure with flexibility to include additional domains or components derived from transcript review. Two qualitative analysts will pilot, revise, and utilize transcript summary templates based on these domains to identify adaptations which will be used to modify content.

Intervention feasibility: We will assess feasibility using three primary criteria: 1) proportion of approached survivors who agree to participate in the intervention trial, 2) adherence to interventions parameters (module/session completion, reasons for dropouts), and 3) acceptability of intervention procedures. For the R61 feasibility trial we aim to enroll 30 participants (10 from each racial/ethnic group: non-Hispanic White, non- Hispanic Black, Hispanic). In an ad hoc manner, if fewer than 50% of approach survivors agree to participate, the intervention will not be considered feasible (i.e., if we need to approach more than 60 survivors to enroll 30 for the feasibility trial). A participant will be considered a “completer” if he/she completes at least 75% of all the sessions (4/6 CBT and 9/12 tDCS sessions). The intervention will be considered feasible if at least 60% of the participants are completers. The feasibility will be assessed in the overall sample of 30 using exact 95% lower confidence bound (Clopper-Pearson method). Thus, the intervention will be considered feasible if 23 or more participants complete the intervention with 95% exact lower confidence bounds (0.61, 1.0). In addition, in an exploratory manner we will assess completion rates in each racial/ethnic group to see if differences are observed. We also will assess treatment acceptability. If >50% of participants report the intervention as ‘unacceptable’ the intervention will not be considered feasible as designed.

Finally, we will estimate preliminary effectiveness of the intervention to inform potential changes to the proposed sample size needed for the larger R33 clinical trial. We will compare mean change scores for pain intensity and functional disability in survivors who received active tDCS vs. sham using a two-sample t-test. Although we will not be powered to detect a statistically significant difference between the groups, we will use the effect estimate to inform power calculations for the R33 clinical trial. If any of the feasibility parameters including 1) participation rate, 2) adherence, or 3) acceptability do not meet our a priori defined feasibility definitions, we will re-engage stakeholders and individuals with lived experiences for input and make adaptions to the interventions based their feedback as well as data we collect from participants related to reasons drop out and unfavorable acceptability. Transition to the R33 phase will be contingent on meeting milestones defined in the Study Timeline. These include: 1) adaptation and tailoring of intervention content, 2) completion of mobile CBT program modifications, and 3) completion of the 6-week feasibility trial of culturally adapted CBT + tDCS.

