1.0 OBJECTIVES

1.1 Primary Objective

1.1.1. To leverage stakeholder input to culturally adapt an evidence-based mobile cognitive behavioral therapy (CBT) intervention for comorbid chronic pain in non-Hispanic Black and Hispanic adolescent survivors, and to obtain input on transcranial direct current stimulation (tDCS) implementation.

Hypothesis: Stakeholder feedback will enable the cultural adaptation of intervention content and delivery for non-Hispanic Black and Hispanic adolescents through identification of tailoring variables and implementation strategies to maximize engagement.

1.1.2. To assess the feasibility of applying a culturally adapted mobile CBT and remote tDCS to a racially/ethnically and geographically diverse sample of non-Hispanic White, non-Hispanic Black, and Hispanic adolescent survivors of pediatric cancer with chronic pain (n=30).

Hypothesis: $\geq 60\%$ of survivors will complete $\geq 75\%$ of the mobile/remote intervention procedures.

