Android and iOS operating systems and is an interactive, self-guided intervention with six core treatment modules. These modules focus on 1) pain education, 2) stress, emotions, and thoughts (e.g., pleasant activity scheduling, thought stopping), 3) relaxation and imagery, 4) lifestyle and school interventions, 5) staying active, and 6) maintenance and relapse prevention. Within the app, participants complete screening questions to set up a profile and evaluate the need for two supplementary treatment modules focused on comorbidities of negative mood and sleep. There are several functional components to the app, including *places and lessons* (each place has 3-5 lessons that provide education and teach pain management skills), *library* (information on skills presented through audio clips, videos), *check-in* (allowing participants to track their pain, activity, mood, and sleep), and *skills tracker* (participants record practicing specific skills such as sleep relaxation). Screen shots from the app are shown in Figure 2. Content is metered according to a time schedule, requiring youth to spend 5 days on skills practice before an assignment can be completed. Components of the program can be used daily (e.g., check in, skills practice). Total treatment duration is approximately 20 min per week over 6 to 8 weeks depending on the number of supplementary modules assigned. The app uses daily reminder notifications to encourage users to log in and complete assigned tasks. If needed, participants will be provided with a mobile device to access the intervention.

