During active sessions participants will receive 1mA direct current flow for 20 minutes. Sham sessions provide a ramp up to 1mA direct flow over a 5 second interval and return to no current flow for the remainder of the session. The tDCS unit requires a unique code for each stimulation session. Each remote session will be monitored for adherence and tDCS device connection quality. If needed, participants will be supplied with a device (iPad, laptop) to allow for video monitoring of the sessions. This methodology is consistent with the approach successfully utilized in our pilot study and ongoing studies. Cultural considerations: While the extent of cultural adaptation that can be applied to tDCS is, unfortunately, limited, we will utilize the above-described focus groups to discuss tDCS. We will conduct a 4th focus group during each phase dedicated exclusively to tDCS procedures. We will solicit feedback from stakeholders on acceptable language to describe tDCS and obtain feedback on study materials (e.g., handouts, images, instructions) and procedures (e.g., family involvement). In our ongoing study, NEUROSTIM, we have made adaptations to tDCS head straps to accommodate different hairstyles and will solicit feedback on the appropriateness of this and other adaptations across cultures.

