Feasibility Study: Eligible participants will be assigned to either culturally adapted mobile CBT + active tDCS to the DLPFC or culturally adapted mobile CBT + sham. For the pilot phase, 10 participants will be enrolled from each racial and ethnic group (non-Hispanic Black, Hispanic, non-Hispanic White), and 5 participants in each group will be allocated to receive active tDCS and 5 to sham tDCS. We will alternate assignment of tDCS location within each group as participants are enrolled using an ABAB design for treatment allocation, separately for each racial and ethnic group. Because this is a feasibility study, blocked randomization and blinding is not necessary, but will be employed in a later study. Participants will complete two 20-minute stimulation sessions per week for 6 weeks. Each week, tDCS sessions will be paired with the mobile CBT program (e.g., core content, practice skills) at a time that is convenient to the participant. Two sessions will not occur within the same 24-hour period. As described above, participants will receive a unique activation code prior to each stimulation session. Each active session will be pre-programmed to deliver 1mA of direct current for 20-minutes; each sham session will be programmed to provide a ramp up to 1mA over a 5 second interval and no current flow for the remainder of the session. tDCS parameters cannot be changed by participants. Adolescents will complete the outcomes measures listed below (e.g., pain intensity, functional disability) and parents will complete measures of SES, anxiety, depression, and their child's medication use at baseline and post-intervention.

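### The completer definition contradicts itself: it asks for at least 75% of sessions but prints 4 of 6 CBT (66.7%), or 13 of 18 (72.2%) with tDCS pooled

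*Combined protocol and SAP*

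**What the plan says.** Section 9.0 (Statistical Considerations, intervention feasibility) makes adherence one of three primary feasibility criteria. A participant is a completer "if he/she completes at least 75% of all the sessions (4/6 CBT and 9/12 tDCS sessions"). The decision rule follows: "Thus, the intervention will be considered feasible if 23 or more participants complete the intervention with 95% exact lower confidence bounds (0.61, 1.0").

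The hypothesis under 1.1.2 sets the same levels, with at least 60% of survivors completing at least 75% "of the mobile/remote intervention procedures". It gives no counts.

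The denominators come from section 4.1. The CBT program is an "interactive, self-guided intervention with six core treatment modules", and in-app screening questions "evaluate the need for two supplementary treatment modules focused on comorbidities of negative mood and sleep". tDCS is given twice a week for 6 weeks, which makes 12 sessions.

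**The concern.** A percentage and a pair of counts in one sentence should describe the same threshold, and here they do not. The tDCS count matches 75% and the CBT count falls below it. The text does not say which governs, whether 75% applies to each component or to the total, or how 4.5 modules should be rounded. The percentage appears in both 1.1.2 and 9.0, the counts only in a parenthesis in 9.0. If the counts govern, the hypothesis in 1.1.2 is not quite the one tested.

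The completer count feeds a fixed pass mark, so a difference of one participant can matter. If the question stays open, it could be settled after the count is known. By section 9.0, missing any feasibility criterion means going back to stakeholders and adapting the intervention, so the result has a practical consequence.

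**Working it through.** **Inputs.** CBT denominator 6 (core modules, 4.1, and the denominator printed in 9.0). tDCS denominator 2 × 6 = 12 (4.1). Threshold 75% (1.1.2 and 9.0). Printed counts 4 and 9, pass mark 23 of 30, lower bound 0.61 (all 9.0).

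**Pass mark, reproduced first.** The one-sided 95% Clopper-Pearson lower bound for k of 30 is the 0.05 quantile of Beta(k, 31 − k):

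- 22 of 30: 0.570, below 0.60 (fail)
- 23 of 30: 0.606, printed as 0.61 (pass)
- 24 of 30: 0.643 (pass)

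So 23 is the smallest passing count. The pass mark is correct and not in dispute.

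**Counts against the percentage.**

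| Reading | Printed minimum | 75% of denominator | Smallest count reaching 75% |
|---|---|---|---|
| CBT alone | 4/6 = 66.7% | 4.5 | 5/6 = 83.3% |
| tDCS alone | 9/12 = 75.0% | 9.0 | 9/12 = 75.0% |
| Pooled | 13/18 = 72.2% | 13.5 | 14/18 = 77.8% |

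The mean of the two component percentages, (66.7 + 75.0)/2 = 70.8%, is also short. Adding supplementary modules to the denominator widens the gap: 4/7 = 57.1% and 4/8 = 50.0%.

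**Who is classified differently.** Enumerate CBT 0–6 by tDCS 0–12, which gives 7 × 13 = 91 combinations, written CBT + tDCS. These are unweighted cells, not probabilities.

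- Printed counts (at least 4 and at least 9): 12 pass.
- 75% of each component (at least 5 and at least 9): 8 pass. The four that drop out are 4+9, 4+10, 4+11 and 4+12, and none are added.
- 75% pooled (total at least 14): 15 pass. 4+9 drops out, and 2+12, 3+11, 3+12 and 6+8 come in.

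**Effect at the pass mark.** Under the per-component reading, k completers by the counts fall below 23 once k − 22 of them have exactly four modules: 1 if k = 23, and 2, 3, 4 or 5 if k = 24, 25, 26 or 27. Under the pooled reading, 23 by the counts including one 4+9 becomes 22 (fail), and 22 by the counts plus one 3+11 becomes 23 (pass).

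**Effect on the chance of passing, per-component reading.** Let p be the true completer rate by the counts and f the share of those completers with exactly four modules. The number reaching 75% of each component is X ~ Bin(30, p(1 − f)). The documents give neither p nor f, so both are assumed.

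| P(X ≥ 23) | f = 0 | f = 5% | f = 10% |
|---|---|---|---|
| p = 80% | 0.76 | 0.57 | 0.37 |
| p = 85% | 0.93 | 0.79 | 0.59 |
| p = 90% | 0.99 | 0.94 | 0.80 |

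**Pooled reading.** The net shift g in the completer rate can go either way, so X ~ Bin(30, p + g). For assumed g of −2.5, 0 and +2.5 percentage points at p = 85%, P(X ≥ 23) is 0.86, 0.93 and 0.97.

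**If CBT keeps pace with tDCS.** Assume one module per two sessions. If the module is credited at the second session of the pair, the only stopping point that separates the versions is after session 9 (4+9). If it is credited at the first, session 9 gives 5+9 and no stopping point separates them.

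**The case against.** The strongest reply is that the operational rule is printed. The counts are given for each component and joined by a conjunction, so every participant can be classified from them, and 75% is probably a loose summary with 4.5 cut to 4. The pooled reading is also the weaker one. The combinations it adds qualify only if the printed counts are set aside. If the counts act as floors, the percentage can only remove completers.

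Divergent participants may be few, because "Each week, tDCS sessions will be paired with the mobile CBT program (e.g., core content, practice skills"). The shares and shifts used above have no source in the documents. The consequence is bounded too: a missed criterion leads to adaptation, and the milestones listed in 9.0 for moving to the R33 phase do not include this threshold.

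Much of this stands. It limits the size of the problem, and it makes the per-component reading the one to plan for. It does not remove the contradiction. An analyst who follows the counts must disregard a percentage that appears in both the hypothesis and the definition, and nothing in the text says to do so. Cutting 4.5 to 4 is incompatible with a minimum of 75%. Pairing does not guarantee equal progress either. CBT is self-guided and its content is metered, "requiring youth to spend 5 days on skills practice before an assignment can be completed", whereas for tDCS "Each remote session will be monitored for adherence and tDCS device connection quality". CBT can therefore lag, and CBT is the component with the inconsistent count.

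**Conclusion.** The concern holds. The printed CBT count is below the stated 75%, and no reading tried (per component, pooled, averaged, or with supplementary modules) makes the counts equal to at least 75%. The error lies in who counts as a completer, not in the 23 of 30 rule.

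That the definition is inconsistent rests on no assumption. How much it matters depends on how many participants finish exactly four modules or, if 75% is read as pooled, fall in the few combinations listed above. The documents do not give that number, so the probabilities show sensitivity and are not forecasts. With no divergent participants there is no effect; at the pass mark one is enough. Because adherence is a primary feasibility criterion, this should be corrected, but it does not threaten the design.

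**What to change.** Make 9.0 and 1.1.2 agree before any completion data are seen, in one of two ways.

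- **(a) Keep 75%.** Define a completer as having at least 75% of CBT modules and at least 75% of tDCS sessions, that is, at least 5 of 6 and at least 9 of 12.
- **(b) Keep the counts.** Define a completer as having at least 4 of 6 (two-thirds) CBT modules and at least 9 of 12 (75%) tDCS sessions, and split the 1.1.2 hypothesis by component in the same way. Do not write 67%: 0.67 × 6 = 4.02, which again requires 5.

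Under either option, say that both components must be met separately and that the six core modules are the CBT denominator, because up to two supplementary modules can be assigned. This treats a CBT session as a core module, which is inferred from the matching denominator of six and should be stated.

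The cost is a wording change in two sections; sample size and the 23 of 30 mark do not change. Option (a) raises the CBT bar by one module relative to the printed count. Option (b) leaves the bar where the counts put it, but the stated CBT criterion falls from 75% to two-thirds and 1.1.2 carries two thresholds instead of one.
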